3. Outcomes	
Primary study outcome: rhythmic abilities in speech and gait (Velocity and Cadence).
 
Secondary study outcome:
 
 • Evaluating the effect of rhythmic interventions on cognition. • Evaluating cortical hemodynamic responses in PD and healthy elderly using functional near-infrared spectroscopy (fNIRS)
4. Study Design:	
Investigator-blinded; Randomized; Controlled; Cross-over.

5. Recruitment

Inclusion Criteria for all groups

- a) The patient is able to cooperate
- b) The patient has the mental competence to provide informed consent to participate in the study
- c) The patient speaks and understands German
- d) The participants are aged between 45-80 yrs. old.

Specific Inclusion Criteria for the DBS Group

- a) Fulfilling the above stated inclusion criteria as stated in a, b, c and d above
- b) The patient is responsive to L-DOPA
- c) Having received or being scheduled for DBS

Exclusion Criteria for all groups

- a) Severe psychiatric disease difficult to treat (compulsive disorder, depression, mania, psychosis, anxiety as outlined in ICD-10 (WHO 2015, current version).
- b) Patient with dementia (DMS-V, MMS<24, MoCa <21)
- c) Secondary Parkinsonism
- d) Age ≤ 18 years
- e) Pregnancy (early onset)
- f) Presence of a known disease other than PD that shortens the life expectancy
- g) Mental incompetence to provide informed consent to participate in the study
- h) Previous intracranial surgery
- i) Epilepsy
- j) Contraindications for DBS seen in MRI-scan (malignant tumors, severe micro vascular disease)
- k) Insufficient skills of German language for participating in neuropsychological evaluations
- l) Sensory problems, severe enough to significantly interfere with neuropsychological assessment
- m) Alcohol and/or drug addiction

5.1 Number of Participants with Power Analysis:	The intended sample size of $N_{\text{total}} = 70$ is based on a small effect size ($\eta^2 = .25$, which is statistically significant increase in the elicitation of words within a certain time) and has been calculated via the statistical programme g*power (power analysis published by the University of Düsseldorf). Further, we expect about 5 drop-outs. Thus, the intended total sample size ($N=70$) may compensate for any possible drop-outs, regardless of group type.
--	---

6. Randomization

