- ii. BDI – Beck's Depression Inventory (1/2)
- iii. BAI – Beck Angst (Fear) Inventar
- iv. MSS – Manie-Selbstbeurteilungsskala (Mania) (1/2)
- v. OCIR – Obsessive-Compulsive Inventory-Revised
- vi. BIS-11 – Barrat-Impulsiveness-Scale (1/2)
- vii. PDQ-39 – Parkinson Quality of Life Questionnaire
- viii. NEO-FFi-30 Items

- ix. AES-S – Apathy Evaluation Scale
- x. PFS-16 – Parkinson-Fatigueskala
- xi. Lebensqualitätsfragebogen (SeiQoI-DW)
- xii. IQ-Code – Questionnaire of cognitive abilities in elderly

8. Interventions

No drugs involved. While speech-language therapy is an established intervention programme in clinical and therapeutic practices, the rhythmic balance-mobility-training (rBMT) has been developed specifically to prevent mobility and balance issues in PD patients and has been evaluated scientifically (see *Parkinson Schweiz* <http://www.redance.ch/page/wirkung/sturzpraevention.html>).

Note that whether or not DBS is performed on a patient is dependent on multiple criteria and can only be decided by the medical team consisting of neurologists, neurosurgeon and neuropsychologists/ psychiatrists. Whether or not DBS is performed on a patient is not part of the study, as it is a normal medical procedure to cure dyskinesia and other motor symptoms arising in Parkinson's disease.

rSLT	
Contents	
 I. 3x 45 Minute sessions per week II. Empathic relationship between patient-therapist III. Specific exercises for the perception and improvement of respiration, phonation, articulation and body posture IV. Rhythmic Exercises according to 'Accent Method' by Sven Smith (1935, 1976)

rBMT	
Contents	
 • 3 x 45 minute sessions per week. • per session: at least 10 songs had to be danced, each with a length ranging from 1:47 - 3:25 Minutes per song. • 1st Week: Level 1. • 2nd Week: Level 1+2. • 3rd Week: Level 2. • 4th Week: Level 2+3.

7. Statistical Analysis

To calculate group differences (i.e. rSLT, rBMT, NT, HC) several univariate ANOVA with post-hoc Bonferroni corrections were performed.

Relationships between speech and gait variables were computed with Spearman's correlations (significance level $p < .05$). The level of statistical significance was set at $p < .05$.

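### Section 5.1 calls eta-squared .25 a small effect; it is a very large one, and N = 70 has only about 10% power for a small effect in a one-way ANOVA

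*Combined protocol and SAP*

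**What the plan says.** Section 5.1 (Number of Participants with Power Analysis) gives an intended total of 70, "based on a small effect size ($\eta^2 = .25$, which is statistically significant increase in the elicitation of words" within a set time. The number "has been calculated via the statistical programme g*power". The section adds "Further, we expect about 5 drop-outs" and concludes that "the intended total sample size ($N=70$) may compensate for any possible drop-outs, regardless of group type". It gives no power target, test family, number of groups, number of measurements or correlation, and does not say whether the 70 include the healthy controls.

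Section 7 (Statistical Analysis) says: "To calculate group differences (i.e. rSLT, rBMT, NT, HC) several univariate ANOVA with post-hoc Bonferroni corrections were performed". On alpha it says: "The level of statistical significance was set at $p < .05". The same section then scores change for each participant, from baseline to 4 weeks and from baseline to 6 months, as a reliable change (RC) score, and bases the further group comparisons on those scores. Section 6 (Randomization) allocates three Parkinson's groups 1:1:1. The healthy controls are a fourth, non-randomised group who took part once.

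**The concern.** The word and the number in section 5.1 contradict each other. A small effect leaves group explaining about 1% of the variance; eta-squared .25 is 25%. With three equal arms it puts the extreme means about 1.2 to 1.4 SD apart.

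Section 5.1 is the only sample-size justification, and the trial is complete, so results will be read against it. A reader who takes it at its word could treat a non-significant comparison as evidence against small effects. In a one-way ANOVA on 70 people, the trial has almost no ability to show them.

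**Working it through.** **Inputs.** N = 70, about 5 drop-outs (so 65 evaluable) and the value .25 come from section 5.1. Alpha .05, the univariate ANOVA and the RC scores come from section 7. The three randomised arms, and the fourth group if controls are counted, come from section 6. Correlation and power target are not in the document, so any value used below is an assumption. The labels small, medium and large for f = .10, .25 and .40 are the usual convention.

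**Formula.** Cohen's f = sqrt(eta² / (1 − eta²)). One-way ANOVA power comes from the noncentral F distribution with lambda = N f² and df = (k − 1, N − k).

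**Step 1: the stated input taken literally.** f = sqrt(.25 / .75) = .577, above the conventional large value of .40. For three equal arms, the range of the means lies between f × 6/sqrt(8) = 1.22 SD and f × sqrt(6) = 1.41 SD.

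**Step 2: does it lead to 70?** The minimum N for 80 / 90 / 95% power is 33 / 42 / 50 with three groups and 37 / 47 / 56 with four. Rounding up to equal groups turns the four-group 37 into 40. At N = 70 the power would be .992 (three groups) or .985 (four). So the literal input does not give 70 with three or four groups at 80 to 95% power. It comes near 70 only with other unstated settings, for example 68 with three groups at 99% power, or 70 with seven groups at 95%.

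**Step 3: other readings of the effect, applied directly to the analysed variable.**

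| Effect | eta² | Power at N = 70, 3 / 4 groups | Power at N = 65, 3 / 4 groups | Equal-group N for 80%, 3 / 4 groups |
|---|---|---|---|---|
| f = .577 | .25 | .99 / .99 | .99 / .98 | 33 / 40 |
| f = .25 (medium) | .059 | .43 / .37 | .40 / .34 | 159 / 180 |
| f = .10 (small) | .01 | .10 / .09 | .10 / .09 | 969 / 1096 |

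**Step 4: one route that does reach 70.** Take G*Power's repeated-measures group-by-time interaction with f = .25, three groups, two time points, correlation .5 and power .95. Then lambda = f² × N × 2 / (1 − .5) = .25 N, and the required N is 65. Adding 5 drop-outs gives 70. Because lambda = .25 N, this equals a one-way ANOVA on change scores with f = sqrt(.25) = .50. Power for three arms is .95 at N = 65 and .96 at N = 70. With correlation .3 it would be .85 and .88.

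**Step 5: sensitivity at 80% power, one-way ANOVA, three randomised arms.**

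- All 65 evaluable are randomised: f about .39, eta² about .135.
- The 70 include an equal share of controls (assumption): 70 × 3/4 = 52.5, so about 52 are randomised, with f about .44 and eta² about .165. This is before drop-out. A proportional loss (65 × 3/4, about 49) raises it to about .174.

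**The case against.** The strongest reply is that the authors probably ran the interaction calculation in step 4 and wrote the wrong symbol. Much of this stands. Section 7 bases further group comparisons on RC scores. With two time points, a one-way ANOVA on change scores is the same F-test as the group-by-time interaction, and dividing every change by one constant standard error leaves F unchanged. On this route 65 + 5 = 70 is coherent and power is about 95%. It still rests wholly on unstated inputs, and it leaves both the symbol and the label wrong.

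It also rules out three stronger readings that a reader might infer:

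- *The trial had only about 40% power.* The 34 to 43% in step 3 holds only if f = .25 applies directly to the analysed variable. If f = .25 was an interaction effect with correlation .5, it is f = .50 on change scores. The document does not settle which.
- *The interaction calculation does not match the planned analysis.* The RC comparisons are change-score comparisons, so it can match them.
- *N = 70 is used both as the requirement and as the number inflated for drop-out.* The statement that 70 "may compensate for any possible drop-outs, regardless of group type" is loose, but it reads naturally as 65 needed plus 5.

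It can also be said that the trial is finished and that all results are to be reported with effect sizes. That limits the harm, but does not make the sensitivity statement right.

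**Conclusion.** The point holds for the sensitivity statement. Eta-squared .25 is not small; if the value was Cohen's f it is medium; and power for a small effect at N = 70 is about 10% (.10 with three groups, .09 with four), assuming f = .10 on the analysed variable and a one-way ANOVA at alpha .05. These results do not depend on which calculation the authors ran.

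What cannot be concluded is that the trial was underpowered for the effect its authors had in mind. That depends on the effect-size metric, the test and the correlation, none of which is given clearly enough. The sensitivity that can be supported is eta-squared of about .135 or about .165 at 80% power, depending on whether healthy controls are counted in the 70.

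**What to change.** In section 5.1:

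1. Delete the word small and correct the effect-size metric (eta-squared or Cohen's f). State the test, number of groups, number of measurements, correlation, alpha and power used.
2. Say whether the 70 include healthy controls.
3. Restate the sensitivity on the scale actually analysed. For a one-way ANOVA at alpha .05 over three randomised arms, 80% power is reached at eta-squared of about .135 (f about .39) if all 65 evaluable patients are randomised. It is reached at about .165 (f about .44) if an equal share of the 70 are controls and about 52 are randomised. Keep the case that applies.
4. If the calculation was the group-by-time interaction, say so with its correlation. Name the between-arm comparison of change from baseline in the first tranche as the analysis it powers.

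The cost is text only: no extra patients and no new data. The stated sensitivity becomes less favourable. As the trial is complete, the correction should be dated and marked as a clarification.

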Clinical Study Protocol

Title:

Effectiveness of specific and intensive speech-language therapy on verbal fluency decline and verbal apraxia symptoms in patients with Parkinson's disease with and without Deep Brain Stimulation (DBS) – a randomized single-blind controlled trial.

Acronym: EILT (Evaluation of Intensive Language Therapy)

EKNZ Nr: 2016-01 428

Clinicaltrial.gov. NR: NCT 029 358 42

Document Created: 30.11.2015

Ethical Approval Obtained: 13.09.2016

Study Start/ First Patient IN: 19.09.2016
Last Patient OUT: 29.06.2018

Study End: 22.10.2018

Final Document update: 09.10.2019

Study Synopsis

1. Background and Rationale:	
In the course of Parkinson's disease (PD) speech and language (SL) deficits may often emerge. In addition, severe verbal fluency (VF) decline has been repeatedly observed in the context of deep brain stimulation (DBS) in PD. While PD non-DBS patients have deficits with respect to loudness and intelligibility of their voice, PD patients who have undergone DBS (PD-DBS) tend rather to suffer from difficulties in semantic and phonemic word retrieval, and from speech apraxia symptoms. However, to-date and to the best of our knowledge, therapeutic approaches focusing specifically on SL deficits observed in PD-DBS patients are yet to be developed and evaluated regarding their effectiveness.

2. Objective(s):	
To evaluate the effectiveness of a high frequency and specific SL therapy compared to an unspecific, non-verbal sham intervention (rhythmic balance-mobility-training (rBMT)), as well as to a 'no therapy'-condition.
 
In more detail:
 
 (1) To compare rhythmic speech and gait of PD-DBS and PD non-DBS patients after different intensive rhythmic intervention programs (rSLT, rBMT and no therapy), as well as against healthy controls (HC) directly after the intervention and again in 6 months (short and long-term effects). 
Secondary objectives:
 
 (1) To examine how speech and language abilities alter due to Parkinson Disease's (PD) by comparing PD-DBS, PD non-DBS and HC (all groups are age-, gender and education-matched). (2) To examine the effect of rhythmic interventions on cognitive abilities. (3) To evaluate measures derived from functional Near Infrared Spectroscopy (fNIRS) as a prognostic marker for verbal and cognitive outcome in PD patients with and without DBS over a period of time.

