Group 1+2+3 were randomized 1:1:1. As a cross-over designed study, PD patients could swap groups once a therapy- tranche has successfully been completed (i.e. BL, intensive therapy, 4 weeks Follow-up, 6 months Follow-up assessments), see Figure 1.

Group 4 were healthy elderly, who did not receive any therapy and participated once.

- Group 1: rhythmic Speech language Therapy (rSLT)
- Group 2: rhythmic Balance-Mobility Training (rBMT)
- Group 3: 'Waiting List', PD patients receiving no therapy
- Group 4: Healthy Controls (HC)

[figure not shown]

Figure 1. Study Design

7. Testing

Testing took place at baseline (BL), at 4 weeks (T1, directly after the end of intensive treatment) and at 6 months (T2 Follow-up).

a. Medical Examination (only at Baseline)

- i. Medical Examination regarding PD-dementia
- ii. Drug/Alcohol Abuse
- iii. Weight, Height, BMI
- iv. Medications
- v. UPDRS – Unified Parkinson's Disease Rating Scale-I (1/1)
- vi. Modified Neurologic Examination according to Hoehn & Yahr
- vii. Falls Efficiency Scale-1 (FES-1)

i. Speech-Language Tests with simultaneous PRAAT Recording (BL, T1, T2)

- i. Reading 'the northwind and the sun'
- ii. Aachner Aphasia Test (AAT): Spontaneous speech
- iii. AAT: Repeating
- iv. AAT: Naming

- v. Regensburgerwortflüssigkeitstest (RWT) complete
- vi. Comprehension of language-specific cues (Gardenpath Experiment)

b. Motor Tests

- One-leg and Tandem standing test (timed via chronometric stop watch in seconds)
- Parkinson Orientated Mobility Assessment (POMA)
- Walking 6 Meters (timed and counting steps)

c. Near-Infrared Spectroscopy (NIRS) (only at BL)

d. Neuropsychological tests/ psychiatric questionnaires (BL, T1 and T2)

Neuropsychological Tests:

- i. MOCA – Montreal Cognitive Assessment
- ii. Clock Test
- iii. CERAD – Boston Naming Test
- iv. CERAD – Word Retrieval (Animals)
- v. BVL – Basel Verbal Learning Test
- vi. BVL – Basel Verbal Learning Test
- vii. ROCF - Rey-Osterrieth Complex Figure
- viii. BVL - Basel Verbal Learning Test
- ix. BVL - Basel Verbal Learning Test - Recognition
- x. Word retrieval (S-Words)
- xi. TMT - Trail Making Test A
- xii. Trail Making Test B
- xiii. Stroop Test
- xiv. WMS-R - Verbal Digit Span
- xv. WMS-R - Corsi Blocks
- xvi. Mosaik-Test
- xvii. BVMT-R – Brief Visuospatial Memory Test-Revised
- xviii. TAP – Alertness
- xix. TAP - Divided Attention
- xx. Delayed Recall BVMT-R
- xxi. Recognition BVMT-R
- xxii. Tulia

Psychiatric Self-Rating Questionnaires:

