Changes in performance were analyzed with the reliable change score (RC). According to Jacobson and Truax (1991) scores are compared on a participant-individual level (e.g. BL with 4 weeks FU, and BL with 6 months FU). Positive scores indicate an improvement in performance, and negative scores indicate a worsening of performance. The RC shows whether a difference in performance is statistically significant on the basis of the reliability of the measurement. Thus, the reliable change score is equivalent to computing a z-score based on standard deviation units.

Further group comparisons are based on the RC scores. All statistical analyses were conducted with SPSS and R. All results are presented with effect sizes.

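### Healthy controls are a fourth level of the only stated group ANOVA, so on raw scores the omnibus F and its effect size mix disease status with therapy; seen once, they can serve only as a fixed reference level

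*Combined protocol and SAP*

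**What the plan says.** The Statistical Analysis section names four levels for its group tests: "To calculate group differences (i.e. rSLT, rBMT, NT, HC) several univariate ANOVA with post-hoc Bonferroni corrections were performed". No other group ANOVA is described, and none is restricted to the three patient arms. The section does not say at which visit, or on which score, this ANOVA is run. It does not list the post-hoc pairs.

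The Randomization section separates the fourth group from the others. On the patient arms it says "Group 1+2+3 were randomized 1:1:1"; on the controls it says "Group 4 were healthy elderly, who did not receive any therapy and participated once".

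The main objective in the Synopsis nevertheless compares the patient groups with each other, "as well as against healthy controls (HC) directly after the intervention and again in 6 months". Secondary objective 1 is a separate question: how PD-DBS, PD non-DBS and matched HC differ in speech and language.

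Change is handled by the reliable change score, for which "scores are compared on a participant-individual level (e.g. BL with 4 weeks FU, and BL with 6 months FU". The section then adds "Further group comparisons are based on the RC scores", without naming the groups. All results are to carry effect sizes.

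**The concern.** Three levels of the factor are treatment assignments made by randomisation. The fourth is a disease status. A single F over all four tests the hypothesis that all four means are equal, and that hypothesis fails as soon as patients differ from healthy people, whatever the therapies do. The Synopsis takes such a difference as its premise, since its rationale is that PD brings speech and language deficits. Matching HC on age, gender and education does not remove it.

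Three things are at stake:

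- The omnibus result, and the effect size reported with it, cannot be read as evidence about therapy.
- If the post-hoc step covers all pairs, three patient-versus-HC pairs join the three randomised ones and the randomised contrasts lose power.
- The primary objective names an HC comparison at two follow-up times, while HC have one visit. The plan does not say how that comparison is made.

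**Working it through.** **Inputs from the documents.** Four ANOVA levels, significance at .05 and Bonferroni post-hoc tests (Statistical Analysis); three randomised arms, HC seen once (Randomization); N = 70 with about 5 drop-outs expected (Number of Participants).

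**Assumptions.** The documents give no group sizes, no HC share of the 70 and no expected patient-HC difference. I take 17 per group (70/4 = 17.5) as the base case and vary the split. I take HC shifts of 0.3 to 1.0 SD, equal variances, and all pairwise post-hoc tests. No figure in the plan addresses this point directly, so there is none to reproduce.

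**Step 1: omnibus F with no therapy effect.** With the three patient means equal and HC shifted by d SD, the noncentrality is

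λ = d² × n_PD × n_HC / N.

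For 17 per group, n_PD = 51, n_HC = 17 and N = 68, so λ = d² × 51 × 17/68 = 12.75 d². The critical value of F(3, 64) at .05 is 2.748. The population eta squared is λ/(λ + N).

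| d (assumed) | λ | P(F significant) | eta squared |
|---|---|---|---|
| 0.3 | 1.15 | 12% | .02 |
| 0.5 | 3.19 | 27% | .04 |
| 0.8 | 8.16 | 63% | .11 |
| 1.0 | 12.75 | 84% | .16 |

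Other splits of 70, at d = 0.5 / 0.8 / 1.0:

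- 10 HC and 20 per patient arm: 19% / 45% / 66%.
- 30 HC and 13 to 14 per patient arm: 36% / 78% / 94%.

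In a simulation of 40,000 trials with 17 per group, the four-group F gave the same 27% / 63% / 84%. An ANOVA of the three randomised arms alone rejected in 4.9% to 5.0% at every shift.

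**Step 2: Bonferroni therapy pairs.** With six pairs, each is tested at .05/6 = .0083. Three of the six compare therapies, so the chance of any false therapy pair is at most 3 × .05/6 = .025. The simulation gave 2.2% to 2.4%, whatever the HC shift. Moving the HC mean changes neither the differences among patient arms nor the within-group SD.

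**Step 3: power of one therapy pair.** For a true 0.8 SD contrast with n per arm, the noncentrality is 0.8 × √(n/2): 2.33 at n = 17 and 2.65 at n = 22. The second size is 65/3 ≈ 22, which applies if the 70 counts patients only, 5 drop out and HC come on top.

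| n per arm | Error term | Power, 3 pairs (.05/3) | Power, 6 pairs (.05/6) |
|---|---|---|---|
| 17 | the two arms only | .43 | .33 |
| 17 | pooled over all groups in the ANOVA | .45 | .36 |
| 22 | the two arms only | .57 | .46 |
| 22 | pooled over all groups in the ANOVA | .58 | .48 |

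The pooled rows use 3n − 3 error degrees of freedom for three groups and 4n − 4 for four equal groups. The loss is about ten percentage points either way.

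**Step 4: what one HC visit allows.** An RC score needs two measurements on the same person. HC have one, so no HC change exists, and any RC comparison can contain only the patient arms. A comparison with HC at 4 weeks or 6 months can then only set patient levels at that visit against the single HC value. Patients are meeting the speech and neuropsychological tests for the second or third time by then, while HC met them once, so HC give no control for retest gains.

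**The case against.** The strongest reply is that the plan already contains the protection. A significant omnibus F is followed by Bonferroni post-hoc tests, which show the pairs that differ. The randomised contrasts are among those pairs and Step 2 shows they are not inflated. A reader might infer from 27%, 63% or 84% that the plan has that rate of false therapy findings. The documents do not support this. Those rates are the F test correctly detecting a real patient-HC difference, and calling them therapy errors presumes that the post-hoc step is ignored.

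A second reply concerns change. Change in performance is assigned to RC scores. HC have none, so those comparisons hold only the randomised arms and carry neither the mixing nor the six-pair penalty. This stands.

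A reader might also infer that the plan promises a change comparison with HC that cannot be carried out. That goes too far. The objective compares speech and gait with HC at two times and mentions neither change nor RC, and the sentence on further RC comparisons names no groups. A comparison of levels can be computed, and whether treated patients approach healthy performance is a fair descriptive question. What stands is that the method is unstated and the comparison has no matching HC visit.

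Finally, the visit of the ANOVA is unstated, so it could be meant for baseline only. In that case the plan specifies no group test of therapy beyond the unnamed RC comparisons, a gap that the same rewording closes.

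**Conclusion.** The point holds in a limited form. HC are a level of the only stated group ANOVA, so on raw scores its F and effect size cannot be interpreted as therapy results: with no therapy effect, significance ranges from 19% to 94% across the splits shown and shifts of 0.5 to 1.0 SD, against 5% for the randomised arms alone. The therapy pairs remain valid but lose about ten points of power at 0.8 SD. RC-based comparisons are unaffected. The follow-up comparison with HC is possible only against one HC measurement, without HC change or retest control.

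The sizes rest on assumed group sizes, assumed patient-HC differences, all-pairs Bonferroni, and the ANOVA being run on raw scores. Because the randomised contrasts stay available and uninflated, this is a correction worth making rather than one that must be made before any result can be used.

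**What to change.** - Test therapy effects in the three randomised patient arms only (rSLT, rBMT, NT), with Bonferroni over those 3 contrasts. State the visit and the score.
- Compare PD-DBS and PD non-DBS with HC at baseline in a separate analysis, labelled non-randomised, for secondary objective 1.
- At 4 weeks and 6 months, show the single HC measurement only as a descriptive reference, and reword the primary objective to say so.
- State that RC comparisons include the patient arms only.

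The cost is revised wording and a re-run on data already collected. The patient-HC contrasts leave the therapy family but keep an analysis of their own.

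### Nothing controls error across the several primary measures and two follow-ups: with 4 to 6 tests the family-wise rate is about 10–26%, depending on assumed count and correlation, not 5%

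*Combined protocol and SAP*

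**What the plan says.** - **Primary outcome** (Synopsis, item 3): "Primary study outcome: rhythmic abilities in speech and gait (Velocity and Cadence"). The speech variable is not named and the measures are not counted or ranked.
- **Timing** (Synopsis, item 2, and section 7, Testing): the main objective compares groups "directly after the intervention and again in 6 months (short and long-term effects"). After baseline, testing is "at 4 weeks (T1, directly after the end of intensive treatment) and at 6 months (T2 Follow-up"). Neither visit is put first.
- **Tests** (section 7, Statistical Analysis): the analysis is introduced with "To calculate group differences (i.e. rSLT, rBMT, NT, HC"), and the method is "several univariate ANOVA with post-hoc Bonferroni corrections were performed". "The level of statistical significance was set at" p < .05.
- **Change scores** (same section): reliable change is computed from baseline to each follow-up, and further group comparisons use those scores.
- **Healthy controls** (section 6, Randomization): this group was seen on one occasion only, so follow-up comparisons involve the three randomised PD arms.

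Nowhere is there a hierarchy, an alpha split across measures or visits, or a requirement that all primary measures succeed.

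**The concern.** A post-hoc Bonferroni correction protects the pairwise group contrasts that follow one ANOVA. It does nothing about running that ANOVA again for another measure or another visit. With several primary measures, two follow-ups and no ranking, a significant result on any one of them can be presented as the trial's primary finding. The stated 5% level then applies to each test but not to the claim that the therapy works on the primary outcome. The section on patient benefit says the evaluation should help doctors and patients choose a therapy, so the error rate of that overall claim is the one that matters.

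**Working it through.** **Inputs from the documents.** Per-test alpha .05; two follow-ups; three randomised arms at 1:1:1; N = 70 with about 5 drop-outs expected (section 5.1). The plan gives no family-wise error rate to reproduce. Its only error figure is the per-test .05, which holds for the main claim only if that claim rests on a single test.

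**Assumptions.** The number of primary measures can be read as two (velocity and cadence only), three (one speech measure plus those two) or four (both quantities for speech and for gait). Three is the natural reading. Correlations between measures and visits are not given, so a range is used.

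**Number of tests.** Two measures × 2 visits = 4; three × 2 = 6; four × 2 = 8.

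**Independent tests.** Family-wise error = 1 − (1 − .05)^k.

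- k = 4: 1 − .95^4 = .185
- k = 6: 1 − .95^6 = .265
- k = 8: 1 − .95^8 = .337

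**Correlated tests.** These values come from simulating three-arm ANOVAs with no true effect, 22 per arm ((70 − 5)/3 = 21.7, if all 70 are PD patients) and one common correlation among all outcomes. A claim is counted when any omnibus F test gives p < .05. The zero-correlation row is from the formula.

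| Assumed correlation | 4 tests | 6 tests |
|---|---|---|
| 0 | 18.5% | 26.5% |
| .3 | about 18% | about 25% |
| .5 | about 16% | about 21% |
| .7 | about 13% | about 17% |
| .9 | about 10% | about 11% |

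A less uniform pattern for six tests (velocity with cadence .8, speech with gait .2, between visits .7) gives 20.2%.

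**Stricter counting.** If a claim also needs a Bonferroni-adjusted contrast among the three arms, six tests give 23–24% when independent and about 10–11% at correlation .9.

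**Check on a remedy.** Suppose Holm is applied to the six omnibus tests, and contrasts within each rejected ANOVA are then tested with Bonferroni from a fresh .05. If rSLT truly differs on all six while rBMT and no therapy do not differ, that null contrast is tested up to six times at .05/3 = .0167. If independent, the error is 1 − (1 − .0167)^6 = .096. Alpha must therefore not be renewed inside each ANOVA.

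**The case against.** **Bonferroni is already used.** It is, but it is described as post hoc in a sentence about group differences. Nothing extends it to measures or visits.

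**The grid of tests is inferred.** This stands in part. A reader might infer that the plan prescribes a separate ANOVA for every primary measure at every follow-up. It does not: it speaks of several ANOVAs without naming outcomes or visits, and only the change-score paragraph ties the analysis to 4 weeks and 6 months. What the documents do show is a plural primary outcome, two visits in the main objective, a .05 level and no rule joining them.

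**The size is not fixed.** This stands. A reader might take 17–26% as the trial's actual error rate. That range assumes exactly six tests and correlations no higher than .7. Velocity and cadence presumably come from the same timed 6-metre walk and are repeated in the same patients, so higher correlation is possible, and the rate could be nearer 10%. With eight independent tests it would be 34%.

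**Four-group ANOVAs give less.** If healthy controls are in each ANOVA, so that Bonferroni covers six pairs, and only contrasts among PD arms count, six tests give about 10–13%. That analysis is not available at follow-up, because the controls have no follow-up data. Even so, it exceeds 5%.

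**The study is exploratory.** The title presents a randomised controlled trial of effectiveness, and the synopsis names a primary outcome. The exploratory label is open to the authors, but the document does not use it.

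**Conclusion.** The omission is clear from the text: no rule controls error across primary measures or follow-ups. If any one significant result counts as a positive primary finding, the family-wise error is about 10–26% for four to six tests, against 5%. Confidence is high for the omission and for the direction. The figure depends on the assumed count and correlation, though no scenario examined brought it down to 5%.

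This does not show that any particular result of the trial is false. It shows that the stated significance level does not apply to the primary claim as a whole.

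**What to change.** 1. List the full primary family: each primary measure, with the speech variable named, at T1 and at T2, compared among the three randomised PD arms only.
2. Apply Holm at an overall .05 across all measure-by-visit-by-contrast p-values. With three measures, two visits and three contrasts there are 18, so the smallest must be below .05/18 = .0028. Alternatively, keep the ANOVA as a gate and carry the alpha allocated to each rejected ANOVA into its contrasts. At the first Holm step that is .05/6 = .0083, or .0083/3 = .0028 per contrast; holding every ANOVA to that share bounds the error over all contrasts at 18 × .05/18 = .05.
3. Label all other tests exploratory, including the speech–gait correlations, and report them with estimates and intervals.
4. Do not now choose a single primary measure, visit and contrast unless a record dated before the data were seen supports it. Last patient out was 29.06.2018, study end 22.10.2018 and the final document update 09.10.2019, and the analysis section is in the past tense. A choice made at this stage could follow the data and would not restore 5%.

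The work is wording plus adjustment of existing p-values; no new data are needed. The price is some power: with six omnibus tests the smallest p-value must be below .0083 rather than .05. A single primary test supported by such a dated record would avoid that loss.
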